4.2 Subgroups

The primary endpoint will be summarized in the subgroups defined by the following:

- sex (female/male)
- **presence of aura during baseline period** (yes/no)
- menstrual-related migraine **at screening** (yes/no)
- **country** (Denmark/Iceland)
- migraine classification **at screening** (EM/CM)
- prior migraine **preventive** treatment failure (yes/no)

The subgroups will be re-examined for appropriateness and may be re-categorized (due to small sample size, for example, if there are < 10% of subjects within a subgroup).

5. Definitions

5.1 Definition of Terms Included in Study Endpoints

5.1.1 Efficacy Endpoints Based on Daily Data Collection

Subjects' daily headache information will be collected through the following questions. The most severe case will be used in the analysis when there are duplicates in the following daily questions. Examples of possible outcomes on migraine-related endpoints are summarized in Table 1:

Table 1. Examples of possible outcomes on migraine-related endpoints.

	Scenario 1	Scenario 2	Scenario 3	Scenario 4	Scenario 5
Daily eDiary questions					
Migraine (Y/N)	Y	Y	Y	N	N
If Y, Peak pain intensity (1 to 10)	1	10	7	NA	NA
Acute medication for migraine (Y/N)	Y	Y	N	Y	Y
If Y, Triptan (Y/N)	Y	N	NA	Y	N
Aura (Y/N)	Y	N	Y	Y	N
Outcomes on migraine-related endpoints					
Migraine day	Yes	Yes	Yes	No	No
Acute headache medication day	Yes	Yes	No	Yes	Yes
Acute migraine-specific medication day	Yes	No	No	Yes	No

Migraine Day

A calendar day (00:00 to 23:59) in which the subject reports any migraine headache or takes any triptan-based acute migraine-specific medication.

Peak Migraine Pain Intensity

Worst or peak pain intensity collected on a migraine headache **which** ranges from 1 to 10 with a higher score indicating more severe pain (**10-point numerical rating scale**).

Acute Headache Medication Day

A calendar day (00:00 to 23:59) in which the subject takes any acute headache medication (AHM)

Acute Migraine-specific Medication Day

A calendar day (00:00 to 23:59) in which the subject takes triptan

Diary Day

A calendar day (00:00 to 23:59) with complete migraine headache, aura, and acute migraine headache medication data recorded in the eDiary device.

Migraine Classification

In subgroup analysis, we will define EM as subjects with < 15 headache days per month at baseline and CM as subjects with ≥ 15 headache days per month at baseline to ensure all subjects belong to either subgroup.

Monthly Frequency Variable in Days

Number of days of interest during **each** monthly interval as defined in [Table 2](#). Monthly frequency variables include

- Monthly migraine days (MMD)
- Monthly acute migraine-specific medication days
- Monthly acute headache medication days

The following proration rule will be applied to all monthly frequency variables for each monthly interval.

Table 2. Calculation for monthly frequency variables within each monthly interval

Within Each Monthly Interval	Monthly Frequency Variable
≥ 14 diary days	Prorate to 28-day equivalent without rounding $\frac{\text{Number of frequency days within each monthly interval}}{\text{Number of diary days within each monthly interval}} \times 28$
< 14 diary days	Set to missing

Monthly Average Peak Migraine Pain Intensity

Peak pain intensity will be collected for **days with migraine headache reported**.

Monthly average **peak** migraine pain intensity is defined as the sum of the **reported peak** pain intensity **scores** during a monthly interval as defined in [Table 3](#) divided by the total number of **reported peak pain intensity scores**. If there is no migraine headache observed during the monthly interval, then the monthly average **peak** migraine pain intensity will be set to 0. If less than 14 days of eDiary data in each monthly interval are recorded, then the monthly average **peak** migraine pain intensity will be set to missing.

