2.1 Objectives and Endpoints

Objectives	Endpoints
Primary	

To explore the relationship between clinical response to erenumab and genetic biomarkers	
Achievement of at least a 50% reduction from baseline in mean monthly migraine days (MMD) over months 4, 5, and 6 in relation to each individual genome-wide significant single-nucleotide polymorphism (SNP) contributing to the migraine polygenic risk score (mPRS)

Objectives	Endpoints
Exploratory	

To describe the relationship between monthly AMSM use and mPRS in erenumab-treated subjects	
Change from baseline in monthly AMSMD over months 4, 5, and 6, in relation to mPRS

To describe the relationship between baseline calcitonin gene-related peptide (CGRP) levels and clinical response with erenumab treatment as assessed by MMD in erenumab-treated subjects	
Change from baseline in MMD over months 4, 5, and 6 in relation to baseline CGRP levelAchievement of at least a 50% reduction from baseline in mean MMD over months 4, 5, and 6 in relation to baseline CGRP levelAchievement of at least a 75% reduction from baseline in mean MMD over months 4, 5, and 6, in relation to baseline CGRP level

To describe the relationship between baseline CGRP levels and clinical response with erenumab treatment as assessed by monthly acute migraine-specific medication days (AMSMD) in erenumab-treated subjects	
Change from baseline in monthly AMSMD over months 4, 5, and 6, in relation to baseline CGRP level

Objectives	Endpoints
Exploratory (Continued)	

• To describe the relationship between mPRS and baseline CGRP	
• mPRS in relation to baseline CGRP level

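### The SAP's definition of a migraine day and its own worked example disagree on a triptan-only day, so the primary responder endpoint can be derived in two ways

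*SAP*

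**What the plan says.** The written definition of a migraine day in SAP section 5.1.1 has two limbs joined by an or: "A calendar day (00:00 to 23:59) in which the subject reports any migraine headache or takes any triptan-based acute migraine-specific medication". An acute migraine-specific medication day is defined separately as "A calendar day (00:00 to 23:59) in which the subject takes triptan".

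Table 1 in the same section applies the definitions to five example days. The relevant rows, Scenarios 1 to 5 from left to right, are:

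- migraine reported: "Migraine (Y/N) Y Y Y N N"
- triptan taken: "If Y, Triptan (Y/N) Y N NA Y N"
- migraine-day outcome: "Migraine day Yes Yes Yes No No"
- acute migraine-specific medication-day outcome: "Acute migraine-specific medication day Yes No No Yes No"

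Migraine days are then summed into MMD: "The following proration rule will be applied to all monthly frequency variables for each monthly interval". The primary endpoint in SAP section 2.1 is "Achievement of at least a 50% reduction from baseline in mean monthly migraine days (MMD) over months 4, 5, and 6", examined against each migraine SNP. Under Appendix B, the sponsor supplies the subject-level endpoint to the genetic analysis group, which codes responders as cases and non-responders as controls.

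**The concern.** Scenario 4 is the only one of the five examples in which the triptan limb changes the answer, and there the table contradicts the text. The SAP therefore holds two workable rules for its most important derived variable: reported migraine or triptan, and reported migraine only. A programmer who codes the text and one who validates against Table 1 would produce different responder flags.

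The effect reaches beyond the primary endpoint. It touches baseline MMD as an outcome and as a covariate (SAP section 4.1 and Appendix B), the analyses relating MMD to CGRP and to the polygenic risk score, and every 50% and 75% responder summary in SAP Table 8. It does not touch acute headache medication days or acute migraine-specific medication days, which have their own consistent definitions. The robustness runs planned in Appendix B add and remove covariates, so they would not show that the endpoint had been derived under the unintended rule.

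**Working it through.** **Step 1: apply each rule to Table 1.** Inputs are the migraine and triptan rows of the table.

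| Scenario | Migraine | Triptan | Text rule (migraine or triptan) | Reported migraine only | Table 1 prints |
|---|---|---|---|---|---|
| 1 | Y | Y | Yes | Yes | Yes |
| 2 | Y | N | Yes | Yes | Yes |
| 3 | Y | NA | Yes | Yes | Yes |
| 4 | N | Y | **Yes** | No | **No** |
| 5 | N | N | No | No | No |

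The text rule reproduces 4 of 5 printed outcomes; the reported-migraine-only rule reproduces 5 of 5. The two medication-day rows match their definitions in all five scenarios and every row has five aligned values, so damage in reading the table is an unlikely explanation. Aura is Y in Scenario 4, but aura is not part of the definition.

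**Step 2: look for a passage that settles it.** Protocol section 8.2.2.1.1 lists the diary items but gives no derivation rule. SAP section 8.3 covers missing diary days, and SAP section 10 (changes from the protocol) is silent. The rule in section 5.1.1 about taking the most severe answer concerns duplicate entries only.

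**Step 3: effect on one subject.** Let h be reported migraine days and t triptan-only days, with subscript 0 for baseline and 1 for the mean of months 4 to 6. With 28 complete diary days the proration factor is 28/28 = 1.

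- Table rule: responder if h1 ≤ 0.5 × h0.
- Text rule: responder if (h1 + t1) ≤ 0.5 × (h0 + t0).

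The left-hand side minus the right-hand side differs between the rules by t1 − 0.5 × t0, so status can flip for subjects near the 50% cut-off, in either direction.

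| Baseline h + t | Months 4–6 h + t | Table rule | Text rule |
|---|---|---|---|
| 8 + 2 | 4 + 2 | (4 − 8)/8 = −50%, responder | (6 − 10)/10 = −40%, non-responder |
| 8 + 0 | 4 + 1 | (4 − 8)/8 = −50%, responder | (5 − 8)/8 = −37.5%, non-responder |
| 8 + 4 | 5 + 1 | (5 − 8)/8 = −37.5%, non-responder | (6 − 12)/12 = −50%, responder |

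**Step 4: how many subjects.** The documents give no frequency of triptan-only days, so this step rests on assumption. Simulations assumed triptan-only days at 5%, 10% or 20% of migraine days. The ranges below cover runs with somewhat different assumed distributions (overall response of about 52% to 54%).

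| Triptan-only days | Change status if they fall in step with migraine days | Change status if they do not fall |
|---|---|---|
| 5% | 3.5% to 3.8% | 5.1% to 5.5% |
| 10% | 5.3% to 5.8% | 8.2% to 8.9% |
| 20% | 7.3% to 8.0% | 13.3% to 14.4% |

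One in-step run used 200,000 subjects. Its baseline was negative binomial (mean 9, size 6, limited to 4–28 days), its proportional reduction Beta(1.5, 1.5), and its counts Poisson. It gave 3.8%, 5.7% and 7.7%. On the planned effective sample of 1400 × 0.9 = 1260 (SAP section 3.2), that is about 47, 72 and 96 subjects, computed from unrounded proportions. The top of the no-fall column gives 0.055 × 1260 ≈ 69, 0.089 × 1260 ≈ 112 and 0.144 × 1260 ≈ 181.

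In the in-step case the overall response rate hardly moves (about 54% under both rules). In the no-fall case it goes from about 52% under the table rule to about 49%, 46% to 47%, and 41% under the text rule.

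**The case against.** The best reply is that a definition outranks an illustration. Table 1 is presented as examples, so the single cell is simply a slip. Section 5.1.1 also collects pain intensity for days on which a migraine headache was reported, which hints that the authors saw migraine days as a wider set. That reading is reasonable but not conclusive: the table is a coherent rule in its own right, and no text says which prevails.

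Second, the protocol and SAP call all analyses descriptive. SAP section 9.1 nevertheless holds the family-wise error rate at 0.05 for the primary endpoint, so its definition still has to be unique.

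Third, one rule applied to everyone yields a different endpoint, not necessarily a misclassified one, and only one set of flags would normally reach the genetic analysis group. This stands in part. The realistic risk is one undocumented choice, or a discrepancy found late in verification. Dilution of SNP odds ratios would follow only if the rule used were not the intended one, and its size has not been calculated.

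Fourth, the magnitudes depend on assumed inputs. This stands. The no-fall column is an upper bound, and it fits poorly with Protocol section 2.3, which lists less use of acute migraine-specific medication among the benefits of treatment.

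**Conclusion.** The SAP is wrong as written: for a day with a triptan and no reported migraine, its text and its table give opposite answers, and nothing in either document resolves them. That conclusion needs no assumption. The number of subjects affected does. With triptan-only days at 5% to 20% of migraine days, roughly 4% to 8% of subjects change responder status if those days fall in step with treatment response, and up to about 14% if they do not fall at all. A stable overall response rate would give no warning, because flips in the two directions can largely cancel in the total while still moving individuals between case and control. It must be fixed because the primary endpoint is not uniquely pre-specified; in an open-label study, choosing the rule after the data are seen would be a post hoc decision.

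**What to change.** Before database lock:

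1. Make the text and table agree. If the written definition is intended, change the Scenario 4 migraine-day cell in Table 1 from No to Yes. If only reported migraines are meant to count, delete the triptan limb from the definition instead. The documents do not establish which was meant, so the sponsor should state it.
2. Use the chosen rule for baseline and for every post-baseline month, and carry it into the endpoint specification supplied to the genetic analysis group.
3. Report the primary endpoint under the other rule as a sensitivity analysis, with a count of subjects whose status differs.

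The correction is one cell or one clause. The sensitivity analysis needs one further derived responder flag, with baseline MMD re-derived under the same rule, and a second run of the primary model in both countries with its meta-analysis. Both diary items are already collected, so no new data are needed.

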5.1 Inclusion Criteria

Subjects are eligible to be included in the study only if all of the following criteria apply:

Before baseline period

- 101 Subject has provided informed consent prior to initiation of any study-specific activities/procedures.
- 102 Age \geq 18 years upon entry into screening
- 103 History of migraine (with or without aura) for \geq 12 months before screening according to the International Headache Society (IHS) Classification ICHD-3 (Headache Classification Committee of the International Headache Society, 2018) based on medical records and/or patient self-report
- 104 \geq 4 headache days that meet criteria as migraine days per month on average across the 3 months before screening

After baseline period

- 105 Must have demonstrated \geq 75% compliance in eDiary usage during baseline period

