5.4 Study Time Intervals

5.4.1 Monthly Intervals for Efficacy Endpoints Derived From Daily Diary Collection

The (4-week) monthly intervals for efficacy endpoints derived from daily eDiary collection will be determined based on each subject's monthly IP dosing dates. When an IP is

missed, discontinued, or no longer required, a 28-day monthly interval will be used. Any eDiary data occurring after EOS date will not be included in the analysis.

Applicable efficacy endpoints utilizing the monthly intervals in **Table 3** include:

- Monthly migraine days (MMD)
- Monthly acute migraine-specific medication days
- Monthly acute headache medication days
- Monthly average migraine pain severity

Table 3. Monthly Intervals for Efficacy Endpoints Derived From Daily Data Collection

Study Period	Assessment Timepoint	Monthly Interval	
		Start Date (Day) ^a	End Date (Day) ^b
Baseline Period	Baseline	Device assignment date	Day prior to study day 1
Open-label Treatment Period	Week 4 (Month 1)	Study Day 1	Week 4 dose date – 1
	Week 8 (Month 2)	Week 4 dose date	Week 8 dose date – 1
	Week 12 (Month 3)	Week 8 dose date	Week 12 dose date – 1
	Week 16 (Month 4)	Week 12 dose date	Week 16 dose date – 1
	Week 20 (Month 5)	Week 16 dose date	Week 20 dose date – 1
	Week 24 (Month 6)	Week 20 dose date	Week 20 dose date + 27

^a Start Date (Day) = End date (day) of previous monthly interval + 1 if IP dose is not received

^b End Date (Day) = Start date (day) of current monthly interval + 27 if IP dose is not received

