Baseline AMSMD in relation to baseline CGRP level	
1. Summary statistics using observed data.2. Estimated slope for CGRP, associated 95% CI and nominal p-value from a linear regression model including age, sex, country (full sample analysis only), and baseline CGRP value as covariate using observed data.3. Spearman correlation between baseline CGRP and baseline AMSMD.
Baseline AHMD in relation to baseline CGRP level	
1. Summary statistics using observed data.2. Estimated slope for CGRP, associated 95% CI and nominal p-value from a linear regression model including age, sex, country (full sample analysis only), and baseline CGRP value as covariate using observed data.3. Spearman correlation between baseline CGRP and baseline AHMD.
Baseline mean migraine severity in relation to baseline CGRP level	
1. Summary statistics using observed data.2. Estimated slope for baseline CGRP, associated 95% CI and nominal p-value from a linear regression model including age, sex, country (full sample analysis only), and baseline CGRP as covariate using observed data.3. Spearman correlation between baseline CGRP and baseline mean migraine severity.
Presence of aura during baseline in relation to baseline CGRP level	
1. Summary statistics using observed data.Estimated odds ratio for baseline CGRP, associated 95% CI and nominal p-value from a logistic regression model including age, sex, country (full sample analysis only), and baseline CGRP using observed data.
Each MFIQ individual domain score (physical function, usual activities, social function, and emotional function) and overall impact usual activities global item score at baseline in relation to baseline CGRP level	
1. Summary statistics using observed data.2. Estimated slope for baseline CGRP, associated 95% CI and nominal p-value from a linear regression model including age, sex, country (full sample analysis only), and baseline CGRP as covariate using observed data.3. Spearman correlation between baseline CGRP and baseline MFIQ score.

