Additionally, this analysis will be performed separately in each of the following subgroups: sex (female/male), presence of aura during baseline period (yes/no), menstrual-related migraine at screening (yes/no), migraine classification at screening (EM/CM), and prior migraine prophylactic treatment failure (yes/no). The subgroups will be re-examined for appropriateness and may be re-categorized (due to small sample size, for example, if there are < 10% of subjects within a subgroup).

Exploratory objectives

1. To explore the relationship between effect of erenumab on AMSMD and the mPRS

Endpoint: Change from baseline in mean monthly AMSMD over months 4, 5, and 6, in relation to the mPRS

Method:

Test for association between the mPRS and the mean change from baseline in monthly AMSMD over months 4, 5, and 6 using linear regression.

2. To describe the relationship between the mPRS and baseline CGRP

Endpoint: The mPRS in relation to baseline CGRP level

Method:

Test for association between the mPRS and baseline CGRP using linear regression. Association between the migraine SNPs and baseline CGRP will also be analyzed. If high skewness is present, baseline CGRP will be transformed using a log-transformation and rank-based inverse normal transformation to assess model robustness. See Exploratory Objective 1.

3. To describe the relationship between the mPRS and migraine disease characteristics

Endpoints:

- mPRS in relation to baseline MMD
- mPRS in relation to baseline AMSMD
- mPRS in relation to baseline acute headache medication days (AHMD)
- mPRS in relation to Migraine Functional Impact Questionnaire (MFIQ) individual domain scores (physical function, usual activities, social function, and emotional function) and overall impact usual activities global item score at baseline
- mPRS in relation to presence of aura during baseline
- mPRS in relation to baseline mean migraine severity

Method:

Test for association between the mPRS and baseline migraine disease characteristic endpoints using linear regression. See Exploratory Objective 1.

4. To describe the relationship between change from baseline in MFIQ score and mPRS in erenumab treated subjects

Endpoint: Change from baseline in MFIQ individual domain scores (physical function, usual activities, social function and emotional function) and overall impact usual activities global item score at month 6, in relation to mPRS

Method:

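### A baseline month with no migraine headache is scored as severity 0, which can distort the exploratory regressions of baseline severity on CGRP and mPRS

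*SAP*

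**What the plan says.** SAP 5.1.1 defines a daily peak pain score that "ranges from 1 to 10 with a higher score indicating more severe pain", collected on days with a reported migraine headache. The monthly value is the sum of the scores divided by their number. Two exceptions follow:

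- With fewer than 14 diary days, the monthly value is missing.
- For an interval without headache the rule begins "If there is no migraine headache observed during the monthly interval, then the monthly average" and ends with "migraine pain intensity will be set to 0".

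SAP 5.4.1 lists "Monthly average migraine pain severity" among the endpoints that use the Table 3 intervals. Baseline is one of these intervals; it runs from device assignment to "Day prior to study day 1". No exception is made for baseline.

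The only severity analyses listed are at baseline:

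- **CGRP** (SAP 9.5, Table 8): a linear regression of severity with CGRP, age, sex and country, plus a "Spearman correlation between baseline CGRP and baseline mean migraine severity".
- **mPRS** (SAP Appendix B, exploratory objective 3): "mPRS in relation to baseline mean migraine severity", by linear regression only.

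The names differ between sections. That 'baseline mean migraine severity' is the 5.1.1 variable taken at baseline is an inference, though no other candidate is defined.

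**The concern.** With no headache there is no score to average, so the mean is 0/0. The rule replaces an undefined quantity by a number below the lowest daily score. A subject with no severity to measure then enters the regression as the mildest case in the study.

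The objective lists migraine frequency (MMD) and severity as separate characteristics. A zero usually marks very low frequency, and neither severity model adjusts for MMD. If CGRP or mPRS is related to frequency, part of that relation can therefore appear in the severity slope. If it is not, the zeros only add variance and pull the slope toward zero.

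**Working it through.** The documents give no figure to reproduce here: no severity mean or SD, no distribution of baseline MMD, and no count of headache-free baselines. What follows is a sensitivity calculation.

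**Can a headache-free baseline enter the analysis?** Yes.

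- Protocol 5.1 (criterion 104) requires at least 4 "headache days that meet criteria as migraine days per month on average across the 3 months before screening". This is history, and no minimum applies to the eDiary baseline.
- Compliance of at least 75% means 0.75 × 28 = 21 diary days or more, so the 14-day rule does not remove such subjects.
- SAP 5.6 has its own percent-change rule for a baseline of 0.

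**How many? (assumed models)**

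- Poisson, every subject averaging exactly 4 days: exp(−4) = 1.8%, or 26 of 1400.
- Poisson at 6 days: 0.25%, or 3.5 subjects. At 8 days: 0.03%, or 0.5.
- A Poisson mixture with every subject's mean at 4 or above: about 2 to 7 subjects.
- Overdispersed negative binomial models that ignore the entry floor: 0.4 to 8%, or 6 to 110 subjects.

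**Inputs.** n = 1400 (SAP 3.2). Assumed: mean m = 6 and SD s = 1.5 or 2 among scored subjects; a fraction f scored 0; correlation r between predictor and frequency; no true link between predictor and severity. A zero lies 6/1.5 = 4 or 6/2 = 3 SDs below the mean.

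**Step 1, precision.** Variance with zeros: V = (1 − f)s² + f(1 − f)m². The interval widens by √V/s − 1.

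Example, f = 0.01, s = 1.5: V = 0.99 × 2.25 + 0.01 × 0.99 × 36 = 2.2275 + 0.3564 = 2.5839. Then √2.5839/1.5 = 1.607/1.5 = 1.07.

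This ignores the slightly smaller n once zeros are missing. Multiplying by √(1 − f) allows for it, and takes about 1 percentage point off at f = 0.02.

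**Step 2, dilution (r = 0).** The expected slope is multiplied by (1 − f), and the test keeps its 5% level. In a separate simulation with a true correlation of 0.1 (mean 6.5, SD 1.5), power was 0.97 without zeros, 0.92 at 1% zeros and 0.89 at 2%.

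**Step 3, spurious association (r > 0).** Let the lowest fraction f of a normal latent frequency be scored 0, and let φ be the normal density at that cut. The covariance between standardised predictor and severity is m·r·φ. The induced correlation is ρ = m·r·φ/√V, and the test statistic shifts by δ = ρ√n. The false-positive rate is P(|Z + δ| > 1.96).

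Example, f = 0.02, s = 1.5, r = 0.2: φ = 0.0484 and √V = 1.706. So ρ = 6 × 0.2 × 0.0484/1.706 = 0.034, δ = 0.034 × 37.4 = 1.27, and the rate is about 25%.

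| Zeros (of 1400) | CI wider, s = 2 to 1.5 | False positives, r = 0.1 | r = 0.2 |
|---|---|---|---|
| 0.25% (3.5) | 1–2% | 5% | 5–6% |
| 0.5% (7) | 2–4% | 5–6% | 6–7% |
| 1% (14) | 4–7% | 6–7% | 9–12% |
| 2% (28) | 8–14% | 8–10% | 17–25% |

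Simulations on the same assumptions agree to within about 1 percentage point. With the zero subjects set to missing, the simulated rate was 4 to 6%.

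**Step 4, rank analysis.** With r = 0.2 and s = 1.5, the simulated Spearman false-positive rate was about 4 to 10% across 0.5 to 2% zeros.

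**The case against.** A reader might infer that both severity analyses are driven by a few impossible values that encode frequency. The documents do not support that, for three reasons:

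- **Driven by a few.** No count is given. At 7 or fewer zeros the interval widens by at most 4% and the false-positive rate is at most about 7%. With the entry floor of 4 days, chronic migraine included and a baseline of up to 35 days, numbers that low are plausible. Reaching 2% takes roughly every subject at exactly 4 days, or a model that ignores the floor. The link between predictor and frequency is also assumed.
- **Impossible.** The 1 to 10 range belongs to the daily score. The monthly value is a derived variable with an explicit convention for no events.
- **Encode frequency.** By the SAP's written definition, a triptan-only day is a migraine day, yet it carries no pain score. MMD can then exceed 0 while severity is 0. (Table 1, scenario 4, labels such a day otherwise.)

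The plan also has partial safeguards. The Spearman correlation treats a zero as merely the lowest rank. SAP 8.5 provides histograms and optional ad-hoc sensitivity analyses. CGRP and mPRS are each analysed against baseline MMD as well.

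All of this limits the size of the problem. It does not defend the rule. The Spearman result leaves the CGRP slope unprotected, and the mPRS analysis has no rank counterpart. A zero produced by the rule is not a data error, so it would normally stay in. The separate MMD analyses help interpretation but do not correct the severity slopes. The triptan-only case also favours missing over 0, since a treated subject would be scored as having no pain.

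**Conclusion.** The rule scores an undefined severity as the lowest value in the data and applies at baseline, where both severity analyses sit. It can distort the linear regressions on CGRP and mPRS; whether it will depends on a count the documents do not give. The effect is small up to about 0.5% zeros. From about 1% the loss of precision becomes noticeable, and a false severity signal becomes a real possibility if the predictor is related to frequency. These sizes rest on the assumed mean, SD, share of zeros and correlation. The point is minor: the endpoints are exploratory, the plan calls its analyses descriptive, the CGRP p-values are nominal, and the primary endpoint does not use this variable.

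**What to change.** In SAP 5.1.1, state that for the baseline severity analyses the monthly average peak pain intensity is missing, not 0, when no pain score is reported in the interval. Tying the condition to the absence of a score also covers triptan-only subjects. Apply the same rule to the variable passed to deCODE for the mPRS analysis. Report the number of such subjects with the baseline characteristics (SAP 9.4). Optionally, show the regressions with the zeros kept as a sensitivity analysis.

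The cost is one sentence and one line in a table. The few subjects with no severity to measure drop out of these analyses, which then describe severity among subjects with at least one scored headache at baseline.
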